6.1.2. Statistical Hypothesis for the Primary Efficacy Endpoint

In the primary efficacy analysis, the SVR12 rate for genotype 1 subjects in each of the two treatment groups will be compared to the performance goal of 50% using a 2-sided exact 1-sample binomial test at the 0.025 significance level. The null (H_0) and alternative (H_1) hypotheses used to assess superiority of SOF/VEL+RBV relative to the performance goal of 50% are:

- H_0 : SVR12 rate = 50%
- H_1 : SVR12 rate \neq 50%

The 50% SVR null rate is derived from SVR rates of 43% (59/137) and 59% (57/96) for treatment naive patients with genotype 1 HCV infection and high viral loads treated with PEG IFN and RBV for 48 weeks cited in the Japanese package inserts for REBETOL® Capsules 200 mg (MSD, July 2015, 19th version) and COPEGUS® Tablets 200 mg (Chugai Pharmaceuticals, July 2015, 6th version), respectively. The weighted average rate then is 50% ((59+57)/(137+96) = 50%).

It is important to note that this historical control rate is a conservative estimate. Because there are no currently available IFN-free treatment options for these subjects and because many of these subjects will have a history of treatment failure with IFN-based therapy and/or medical comorbidities precluding the use of IFN, the actual response rate of this population would likely be much lower than 50%.

No statistical hypothesis testing will be performed in genotype 2 subjects.

6.1.3. Primary Analysis of the Primary Efficacy Endpoint

The 2-sided exact 1-sample binomial test will be used to test the statistical hypotheses described above. The 2-sided 95% exact confidence interval (CI) based on the Clopper-Pearson method {Clopper 1934} will be provided for the SVR12 rate for each of the two treatment groups and HCV genotype (1[1a, 1b, 1 other], 2, and total).

6.1.4. Subgroup Analysis of the Primary Efficacy Endpoint

Point estimates and 95% exact CIs of the SVR12 rates for each treatment group will be displayed by HCV genotype (1[1a, 1b, 1 other], 2, and total). Subgroups are outlined in Section 3.4.

6.2. Secondary Efficacy Endpoints

6.2.1. Definition of Secondary Efficacy Endpoints

Secondary efficacy endpoints include the following:

- The proportion of subjects who attain SVR at 4 and 24 weeks after cessation of treatment (SVR4 and SVR24)
- The percentage of subjects with HCV RNA < LLOQ while on treatment by study visit
- HCV RNA (\log_{10} IU/mL) and change from baseline in HCV RNA (\log_{10} IU/mL) through end of treatment (EOT)
- The percentage of subjects with virologic failure as the following:
 - On-treatment virologic failure
 - HCV RNA \geq LLOQ after having previously had HCV RNA < LLOQ, while on treatment, confirmed by 2 consecutive values (Note: second confirmation value may be posttreatment) or last available on-treatment measurement with no subsequent follow-up values (ie, breakthrough)
 - $> 1 \log_{10}$ IU/mL increase in HCV RNA from nadir while on treatment, confirmed by 2 consecutive values (Note: second confirmation value may be posttreatment) or last available on-treatment measurement with no subsequent follow-up values (ie, rebound)
 - HCV RNA persistently \geq LLOQ through 8 weeks of treatment (ie, nonresponse)
 - Relapse
 - HCV RNA \geq LLOQ during the posttreatment period having achieved HCV RNA < LLOQ at EOT, confirmed by 2 consecutive values or last available posttreatment measurement
- Characterization of HCV drug resistance substitutions at baseline, during, and after therapy with SOF/VEL+RBV

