3.8.2. Analysis Windows

Subject visits might not occur on protocol-specified days. Therefore, for the purposes of analysis, observations will be assigned to analysis windows.

In general, the baseline value will be the last nonmissing value on or prior to the first dose date of study drug.

HCV RNA, vital signs, and safety laboratory data collected up to the last dose date + 3 days are considered to be on-treatment data and HCV RNA, vital signs, and safety laboratory data collected after the last dose date + 3 days are considered posttreatment data. The analysis windows for on-treatment HCV RNA, vital signs and safety laboratory data are provided in Table 3-1.

Table 3-1. Analysis Windows for On-treatment HCV RNA, Vital Signs and Safety Laboratory Data

Nominal Visit	SOF/VEL + RBV 12 Weeks			SOF/VEL + RBV 24 Weeks		
	Nominal Day	Lower Limit	Upper Limit	Nominal Day	Lower Limit	Upper Limit
Baseline	1	(none)	1	1	(none)	1
Week 1	7	2	11	7	2	11
Week 2	14	12	18	14	12	18
Week 3	21	19	25	21	19	25
Week 4	28	26	32	28	26	32
Week 5	35	33	39	35	33	39
Week 6	42	40	49	42	40	49
Week 8	56	50	63	56	50	63
Week 10	70	64	77	70	64	77
Week 12	84	78	≥ 85	84	78	98
Week 16	NA	NA	NA	112	99	126
Week 20	NA	NA	NA	140	127	154
Week 24	NA	NA	NA	168	155	≥ 169

HCV RNA, vital sign, and safety laboratory data collected after the last dose date + 3 days will be assigned to the posttreatment follow-up (FU) visit. Visit windows will be calculated from the last dose date (ie, FU Day = collection date minus the last dose date) as shown in Table 3-2.

Table 3-2. Analysis Windows for Posttreatment HCV RNA, Vital Signs and Safety Laboratory Data

Nominal FU ^a Visit	HCV RNA/Vital Sign			Vital Signs and Safety Laboratory Data ^b		
	Nominal FU Day	Lower Limit	Upper Limit	Nominal FU Day	Lower Limit	Upper Limit
FU-4	28	21	69	28	4	30
FU-12	84	70	146	NA	NA	NA
FU-24	168	147	210	NA	NA	NA

a FU-x visit = posttreatment Week-x follow-up visit.

b Vital signs and safety labs will only be summarized for the FU-4 visit (up to 30 days after last dose).

ECG data is collected at baseline only. Qualitative assessments of whether the ECG is normal or abnormal will be assessed at baseline.

3.8.3. Selection of Data in the Event of Multiple Records in an Analysis Window

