6.2.2. Analysis Methods for Secondary Efficacy Endpoints

For analyses of HCV RNA < LLOQ by visit while on treatment and during the posttreatment (SVR) follow-up period, subjects will be assigned a value at each visit based on the analysis visit windows specified in Section 3.8.2. Missing values will be imputed based on the categorical imputation rules described in Section 3.6.1. The two-sided 95% exact confidence interval based on the Clopper-Pearson method will be provided by HCV genotype (1[1a, 1b, 1 other], 2, and total) for the percentage of subjects with HCV RNA < LLOQ at each visit within each treatment

group and total. The overall category for “HCV RNA < LLOQ” will be divided into the following 2 subcategories: “< LLOQ TND” for subjects with target not detected and “< LLOQ detected” for subjects with < LLOQ in tabular displays.

Graphs for the percentage of subjects with HCV RNA < LLOQ over time during treatment will be displayed by HCV genotype (1[1a, 1b, 1 other], 2, and total).

Summary statistics will be presented for absolute values and change from baseline in HCV RNA (\log_{10} IU/mL) by HCV genotype (1[1a, 1b, 1 other], 2, and total) and visit through EOT.

Imputation rules described in Section 3.6.1 will be used to assign HCV RNA values for missing values at visits that are bracketed by “< LLOQ TND” and/or “< LLOQ detected”. Otherwise, a missing = excluded analysis will be performed. Plots of the mean \pm SD and median (Q1, Q3) of absolute values and changes from baseline in HCV RNA through EOT will be presented by HCV genotype (1[1a, 1b, 1 other], 2, and total).

For the SVR12 endpoint analysis, a summary table of the number and percentage of subjects with SVR12, virologic failure (VF), and Other will be created by HCV genotype (1[1a, 1b, 1 other], 2, and total). All subjects who achieved SVR12 will be categorized as SVR12. Virologic failure will be descriptively summarized as “on-treatment virologic failure” and relapse (which will be broken down by study drug completed yes/no). Subjects who do not achieve SVR12 and do not meet criteria for virologic failure will be categorized as “Other”. The denominator for relapse will be the number of subjects who had HCV RNA < LLOQ on their last observed on-treatment HCV RNA measurement; otherwise, the denominator will be the number of subjects in the FAS.

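### A posttreatment recurrence that follows an unconfirmed last on-treatment value at or above LLOQ meets no virologic-failure definition and is counted as 'Other'

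*SAP*

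**What the plan says.** The proportion with virologic failure is a secondary objective and endpoint in both documents (Protocol 2 and 8.1.3; SAP 1.1 and 6.2.1). SAP 6.2.1 gives four routes to it.

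- **Breakthrough:** HCV RNA at or above LLOQ after earlier suppression, "confirmed by 2 consecutive values (Note: second confirmation value may be posttreatment) or last available on-treatment measurement with no subsequent follow-up values (ie, breakthrough").
- **Rebound:** a rise of more than 1 log10 from nadir, with the same confirmation rule.
- **Nonresponse:** HCV RNA never below LLOQ through 8 weeks of treatment.
- **Relapse:** HCV RNA at or above LLOQ "during the posttreatment period having achieved HCV RNA < LLOQ at EOT, confirmed by 2 consecutive values or last available posttreatment measurement".

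End of treatment has no separate operational definition. SAP 6.2.2 supplies one through the denominator: "The denominator for relapse will be the number of subjects who had HCV RNA < LLOQ on their last observed on-treatment HCV RNA measurement". SAP 3.8.2 draws the boundary: "HCV RNA, vital signs, and safety laboratory data collected up to the last dose date + 3 days are considered to be on-treatment data".

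SAP 6.2.2 then sorts every subject into SVR12, virologic failure or a remainder, with SVR12 taking precedence. "Subjects who do not achieve SVR12 and do not meet criteria for virologic failure will be categorized as" *Other*.

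**The concern.** The on-treatment rules and the relapse rule do not quite meet. The on-treatment rules let go of a last on-treatment value at or above LLOQ once the next value is below LLOQ. The relapse rule still excludes the subject because of that same value. If the virus then returns, no rule picks it up.

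In a retreatment trial, the SVR12 / virologic failure / *Other* table is where a reader separates failure of the drugs against the virus from missing data and dropout. A documented recurrence placed in *Other* is reported as non-virologic, and it is absent from both the relapse numerator and its denominator. Within this sequence, the error can only lower the virologic-failure count.

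**Working it through.** **Plan's own figures.** The plan states no expected relapse or virologic-failure rate, so this endpoint has no figure to reproduce. The one design figure is over 90% power with 45 genotype 1 subjects per arm (SAP 1.3). It reproduces: with 50% under the null and two-sided 0.025, the test rejects at 31 or more of 45 (upper tail 0.0080), and power at 77% is 92.5%. The point does not depend on it; only the arm size is used below.

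**A worked subject.** Week 10 below LLOQ; Week 12 (last on-treatment) 20 IU/mL; posttreatment Week 4 below LLOQ; posttreatment Weeks 12 and 24 at 10^6 IU/mL. SAP 3.7 sets values below LLOQ to 15 − 1 = 14 IU/mL.

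| Definition | Met? | Reason |
|---|---|---|
| Breakthrough | No | Next value is below LLOQ, and follow-up exists |
| Rebound | No | log10(20/14) = 0.155, below 1. At 200 IU/mL the rise is log10(200/14) = 1.155, but unconfirmed |
| Nonresponse | No | Suppressed earlier |
| Relapse | No | Last on-treatment value is at or above LLOQ |
| SVR12 | No | Posttreatment Week 12 is at or above LLOQ |

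The result is *Other*.

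**How wide the gap is.** Take a subject suppressed earlier whose last on-treatment value is at or above LLOQ. Let each of posttreatment Weeks 4, 12 and 24 be below LLOQ, at or above LLOQ, or missing: 3 × 3 × 3 = 27 patterns. Of these, 19 contain a posttreatment value at or above LLOQ:

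- 10 are breakthrough. The first observed posttreatment value is at or above LLOQ and confirms the last on-treatment value.
- 5 are SVR12, because posttreatment Week 12 is below LLOQ.
- 4 are *Other*. Week 4 is below LLOQ and virus is present at Week 12, or at Week 24 with Week 12 missing.

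Check: 10 + 5 + 4 = 19. In 3 of the 4, the recurrence is confirmed or is the last available value. The fourth (below, above, below) has a single unconfirmed Week 12 value. It would be *Other* even with suppression at end of treatment, so it is not part of the gap.

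**Retest timing.** Protocol 3.4.1 requires confirmation of an on-treatment signal within 2 weeks. Suppose the signal is on the day of last dose, the retest is below LLOQ, and posttreatment Weeks 4 and 12 are at or above LLOQ. A retest on day 3 after last dose is on-treatment, becomes the last on-treatment value, and makes the subject a relapse. A retest on day 4 is posttreatment, and the subject is *Other*.

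**Size per subject.** The virologic-failure percentage uses the FAS as denominator: 1/45 = 2.2 points in a genotype 1 arm, 1/55 = 1.8 points in a whole arm.

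**The case against.** The strongest reply is that the gap is small and the plan closes most of it. That is right.

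- A reader might infer that any single end-of-treatment value at or above LLOQ slips through. It does not. If the next value is also at or above LLOQ, breakthrough applies, because the confirming sample may be posttreatment. If there is no follow-up, breakthrough applies through the clause "last available on-treatment measurement with no subsequent follow-up values". If a retest by last dose + 3 days is below LLOQ, later viremia is already relapse.
- A reader might call it perverse that an isolated value with no follow-up counts as failure while one followed by suppression does not. That contrast is coherent: the first is a worst-case rule for missing data, the second an unconfirmed signal. What is missing is a rule for the recurrence afterwards.
- A reader might add that subjects suppressed at end of treatment with no posttreatment sample dilute virologic failure. SAP 6.2.2 uses the special denominator for relapse only, so the virologic-failure percentage cannot be affected. Keeping those subjects is an openly stated convention, and SAP 4.1 counts them separately.
- A reader might extend the gap to subjects who stop early without ever being suppressed on treatment. Whether a later return of virus in them is relapse or failure after premature discontinuation is a matter of judgement, and the documents give no frequency for it.
- The viremia is not hidden. A further table in SAP 6.2.2 shows observed and imputed results at or above LLOQ at each posttreatment visit.

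What survives is the single sequence. For it, the residual rule gives a definite and wrong label.

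**Conclusion.** The point holds in this narrow form and is minor. A subject suppressed earlier on treatment, with an unconfirmed last on-treatment value at or above LLOQ, a next value below LLOQ, and then a recurrence that is confirmed or is the last available value, is reported as *Other* although virologic failure is documented. Each such subject costs the virologic-failure percentage 2.2 points in a genotype 1 arm or 1.8 points in a whole arm. The documents give no frequency for the sequence, and it may not occur at all.

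The assumptions are planned arm sizes, end-of-treatment status read from the last observed on-treatment sample, and consecutive values read as consecutive observed values. The last matters only for unscheduled retests: an analyst who used visit-window values alone would ignore a retest before day 21 after last dose, where the posttreatment Week 4 window opens (SAP Table 3-2). The worked subject is *Other* under either reading.

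The documents do not support reading this as a flaw in the primary analysis: the subject fails SVR12 either way. Nor is it a contradiction, because the relapse numerator and denominator agree with each other. A rule is missing.

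**What to change.** Keep the relapse definition in SAP 6.2.1 and add one sentence:

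> *Relapse also includes posttreatment HCV RNA at or above LLOQ, under the same confirmation rule, in a subject who was below LLOQ earlier on treatment and whose last on-treatment value at or above LLOQ was not confirmed because the next value was below LLOQ.*

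In SAP 6.2.2, add to the relapse denominator every subject below LLOQ earlier on treatment who had such an unconfirmed last on-treatment value followed by a value below LLOQ, whether or not they later relapse. The precedence of SVR12 stays as it is.

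The cost is two sentences and a small programming change, with no new data. SAP 1 has the plan finalized before database finalization, which is the time to do it.

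The downside is small: the relapse denominator differs slightly from the one now stated, so the relapse rate can move either way. As an illustration with assumed counts, start from 4/44 = 9.1%. One added subject who reaches SVR12 gives 4/45 = 8.9%; one who recurs gives 5/45 = 11.1%. The virologic-failure count itself can only stay the same or rise.

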6.2.2. Analysis Methods for Secondary Efficacy Endpoints

For analyses of HCV RNA < LLOQ by visit while on treatment and during the posttreatment (SVR) follow-up period, subjects will be assigned a value at each visit based on the analysis visit windows specified in Section 3.8.2. Missing values will be imputed based on the categorical imputation rules described in Section 3.6.1. The two-sided 95% exact confidence interval based on the Clopper-Pearson method will be provided by HCV genotype (1[1a, 1b, 1 other], 2, and total) for the percentage of subjects with HCV RNA < LLOQ at each visit within each treatment

group and total. The overall category for “HCV RNA < LLOQ” will be divided into the following 2 subcategories: “< LLOQ TND” for subjects with target not detected and “< LLOQ detected” for subjects with < LLOQ in tabular displays.

Graphs for the percentage of subjects with HCV RNA < LLOQ over time during treatment will be displayed by HCV genotype (1[1a, 1b, 1 other], 2, and total).

Summary statistics will be presented for absolute values and change from baseline in HCV RNA (\log_{10} IU/mL) by HCV genotype (1[1a, 1b, 1 other], 2, and total) and visit through EOT.

Imputation rules described in Section 3.6.1 will be used to assign HCV RNA values for missing values at visits that are bracketed by “< LLOQ TND” and/or “< LLOQ detected”. Otherwise, a missing = excluded analysis will be performed. Plots of the mean \pm SD and median (Q1, Q3) of absolute values and changes from baseline in HCV RNA through EOT will be presented by HCV genotype (1[1a, 1b, 1 other], 2, and total).

For the SVR12 endpoint analysis, a summary table of the number and percentage of subjects with SVR12, virologic failure (VF), and Other will be created by HCV genotype (1[1a, 1b, 1 other], 2, and total). All subjects who achieved SVR12 will be categorized as SVR12. Virologic failure will be descriptively summarized as “on-treatment virologic failure” and relapse (which will be broken down by study drug completed yes/no). Subjects who do not achieve SVR12 and do not meet criteria for virologic failure will be categorized as “Other”. The denominator for relapse will be the number of subjects who had HCV RNA < LLOQ on their last observed on-treatment HCV RNA measurement; otherwise, the denominator will be the number of subjects in the FAS.

A concordance table between SVR12 and SVR24 will be provided by HCV genotype (1[1a, 1b, 1 other], 2, and total) for each treatment group and total. Subjects with both observed SVR12 and observed SVR24 data will be included for this analysis.

In addition, a summary table of the number and percentage of subjects with HCV RNA < LLOQ and \geq LLOQ at the posttreatment follow-up visit (observed and imputed, with reasons for imputed) will be provided by HCV genotype (1[1a, 1b, 1 other], 2, and total) for each posttreatment follow-up visit; 95% Clopper-Pearson exact CIs will be presented for the overall proportion of subjects with HCV RNA < LLOQ.

Drug resistant substitutions will be analyzed as part of the Virology Study Report.

6.3. Exploratory Efficacy Endpoints

6.3.1. Definition of Exploratory Efficacy Endpoints

Exploratory efficacy endpoints may include:

6.3.2. Analysis Methods for Exploratory Efficacy Endpoints

PPD

6.4. Changes From Protocol-Specified Efficacy Analyses

There are no planned changes from protocol-specified efficacy analyses.

7. SAFETY ANALYSES

7.1. Adverse Events and Deaths

7.1.1. Adverse Event Dictionary

Clinical and laboratory adverse events (AEs) will be coded using the current version of MedDRA. System organ class (SOC), high level group term (HLGT), high level term (HLT), preferred term (PT), and lower level term (LLT) will be provided in the AE dataset.

7.1.2. Adverse Event Severity

Adverse events are graded by the investigator as Grade 1, 2, 3, or 4 according to toxicity criteria specified in the protocol. The severity grade of events for which the investigator did not record severity will be categorized as “missing” for tabular summaries and data listings, and the most severe will be considered (for sorting purpose only) in data presentation.

7.1.3. Relationship of Adverse Events to Study Drug

Related AEs are those for which the investigator selected “Related” on the AE eCRF to the question of “Related to Study Treatment.” Events for which the investigator did not record relationships to study drug will be considered related to study drug for summary purposes. However, by-subject data listings will show the relationship as missing from that captured on the eCRF.

7.1.4. Serious Adverse Events

Serious adverse events (SAEs) will be identified and captured as SAEs if AEs met the definitions of SAE specified in the study protocol. Serious adverse events captured and stored in the clinical database will be reconciled with the SAE database from the Gilead Drug Safety and Public Health Department before database finalization.

7.1.5. Treatment-Emergent Adverse Events

7.1.5.1. Definition of Treatment-Emergent

Treatment-emergent adverse events (TEAEs) are defined as one or both of the following:

- Any AEs with an onset date on or after the study drug start date and no later than 30 days after permanent discontinuation of study drug.
- Any AEs leading to premature discontinuation of study drug.

7.1.5.2. Incomplete Dates

If the onset date of an AE is incomplete, then the month and year (or year alone if month is not recorded) of onset will determine whether an AE is treatment emergent, as long as the AE stop date is not prior to the first dose date of study drug. The event will be considered treatment emergent if both of the following 2 criteria are met:

- The AE onset and end dates are the same as or after the month and year (or year) of the first dose date of study drug
- The AE onset date is the same as or before 30 days after the date of the last dose of study drug

An AE with completely missing onset and stop dates, or with the onset date missing and a stop date later than the first dose date of study drug, will be considered to be treatment emergent.

7.1.6. Summaries of Adverse Events and Deaths

A brief high-level summary of TEAEs will be provided by treatment group and total and by the number and percentage of subjects who had the following: any AE, any AE of Grade 3 or above, any AE of Grade 2 or above, any treatment-related AE, any treatment-related AE of Grade 3 or above, any treatment-related AE of Grade 2 or above, any SAE, any treatment-related SAE, any AE that led to premature discontinuation of any study drug, any AE that led to premature discontinuation of SOF/VEL, any AE that led to premature discontinuation of RBV, any AE that led to premature discontinuation of all study drugs, any AE that led to modification or interruption of any study drug, any AE that led to interruption of SOF/VEL, any AE that led to modification or interruption of RBV, any AE that led to modification or interruption of all study drugs. All deaths (including those that were treatment emergent and those that were not treatment emergent) observed during the study will also be summarized and included in this table.

A brief summary of AEs by age group (ie, <65 years, ≥65 years) and by cirrhosis status will also be explored.

Adverse event summaries will provide the number and percentage of subjects with TEAEs by SOC and PT, by age group, by treatment group and total based on the Safety Analysis Set as follows:

- All AEs
- AEs of Grade 3 or above
- AEs of Grade 2 or above
- All treatment-related AEs

- Treatment-related AEs of Grade 3 or above
- Treatment-related AEs of Grade 2 or above
- All SAEs
- All treatment-related SAEs
- AEs leading to premature discontinuation of any study drug
- AEs leading to premature discontinuation of SOF/VEL
- AEs leading to premature discontinuation of RBV
- AEs leading to premature discontinuation of all study drugs
- AEs leading to modification or interruption of any study drug
- AEs leading to interruption of SOF/VEL
- AEs leading to modification or interruption of RBV
- AEs leading to modification or interruption of all study drugs

Multiple events will be counted once only per subject in each summary. Adverse events will be summarized and listed first in alphabetic order of SOC and then by PT in order of descending incidence in the overall group within each SOC. In summaries by severity grade, the most severe grade will be used for those AEs that occurred more than once in an individual subject during the study.

In addition to the above summary tables, TEAEs will also be summarized by PT only, in order of descending incidence for:

- AEs that occurred in at least 5% of subjects
- AEs of Grade 3 or above
- All treatment-related AEs
- All SAEs
- AEs leading to premature discontinuation of any study drug
- AEs leading to premature discontinuation of SOF/VEL
- AEs leading to premature discontinuation of RBV
- AEs leading to premature discontinuation of all study drugs
- AEs leading to modification or interruption of any study drug

- AEs leading to interruption of SOF/VEL
- AEs leading to modification or interruption of RBV
- AEs leading to modification or interruption of all study drugs

In addition to the by-treatment summaries described above, data listings will be provided for the following:

- All AEs
- AEs of Grade 3 or above
- SAEs
- Deaths
- AEs leading to premature discontinuation of any study drug
- AE with changes other than resolution dates between the SVR12 and SVR24 analyses (provided only at the final analysis)

